5.2 Analysis methods

Subgroup analyses

The following pre-specified subgroup analyses will be conducted:

1. Baseline TNS: 9-28 vs 0-8
2. Diabetic vs not diabetic
3. Gender: M/ F
4. Baseline access type: AVF vs other (including graft/ catheter)
5. Dialysis vintage at randomisation: <12 months v ≥12 months

The access type will be separated into AVF verses other as the clear majority of participants (78%) were using an AVF at baseline. Baseline blood flow rate was considered for subgroup analysis but discarded as there was little variation across the cohort (baseline blood flow rate

median 300, 5th percentile 300, 95th percentile 330). Sub-group analyses will be completed by including an interaction between each sub-group and the treatment variable.

5.2. Secondary/SAEs outcomes

A summary of each secondary or safety endpoint will be provided. Continuous outcomes will be summarised by their mean (SD), while binary outcomes will be summarised by percentages.

Continuous: All continuous secondary endpoints without repeated measurements will be analysed using linear regression adjusted with its baseline counterpart. This applies to the exploratory analyses

Continuous repeated measurements: All secondary outcomes repeatedly measured over time (Secondary outcomes 1a, 1c, 1e) will be modelled using a Linear Mixed model including random intercept, randomisation and time categories as per the analysis of the main outcome (5.1). The Linear Mixed model will be formulated to use Direct Likelihood, which will allow for data that is missing at random.

Binary repeated measurement: will be analysed using generalised linear mixed model with a logit link and a binary distribution (logistic regression), for Secondary outcomes 1b and 1d.

Count: Count secondary endpoints, such as number of reported access-related AEs, will be modelled using a Poisson regression model, and a negative binomial model if there is overdispersion (>1.3). This will apply for secondary outcomes 2b, 2c, 2e, 2f, 2g, 2h.

Survival time: Survival curves and estimated median survival time will be generated according to the Kaplan-Meier method. Log-rank test will be used to assess the difference between the two survival curves by secondary endpoint. The hazard ratio between two treatments will be estimated with a Cox Proportional Hazards model if the PH assumption is met. This will apply for Secondary outcomes 2a and 2d.

Composite Rank Score: A rank-based procedure combining mortality and functional neuropathy score will be used (Secondary outcome 4). Patients who die before the 48 month follow-up will be ranked from lowest (poorest outcome) to highest on their survival time (less survival time=lower rank). Then, those who are alive at the final follow-up with a TNS will be ranked from least to most favourable change in TNS from baseline (TNS follow-up – TNS baseline) . If participants are alive but do not have a valid TNS then they will be censored (Shortest Survival < Longest Survival < Lowest TNS change < Highest TNS change). Ranks between treatment groups will be compared with a log-rank test, and hazard ratio (with 95% confidence intervals) will be estimated with Cox proportional hazards regression. The main assumption underlying the composite ranking is that death at any time is worse than the greatest increase in TNS.

Sensitivity test for missing data in the main outcome: A sensitivity analysis of the missing at random assumption in the main outcome will be made with a delta-adjustment tipping point analysis. If a significant difference is found between the groups we will use a marginal delta adjustment method with a tipping point. We will impute missing visits (using a non-monotone MCMC method), then add a constant (delta) to the imputed data until the difference is no longer significant ($p>0.05$). If the value of delta required to overturn significant results is implausible then we will consider the results to be robust.

Further analyses: Further analyses for the cohort phase of the study will be subject to a separate report when data is available.

Serious adverse event outcomes:

Serious adverse event outcomes will be independently categorized by two authors into the following groups (as defined above):

- Access failure
- Septicaemia
- Cardiovascular event
- Surgery for carpal tunnel syndrome
- Parathyroidectomy surgery
- Fractures requiring or occurring during a hospital admission
- Other

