2.2 Randomization

Participants were randomised to receive either haemodiafiltration or standard high flux haemodialysis. Participants were randomised in a 1:1 fashion with stratification by baseline neuropathy score. Strata 1 was defined as TNS score 0-8 (no to minor neuropathy) and strata 2 as TNS score 9-28 (moderate to severe neuropathy). The allocation sequence was based on blocks of 4 and generated centrally by an independent statistician who had no other involvement in the study. To ensure allocation concealment, randomisation was performed by an independent university employee based in a physically separate site with no other involvement in the study. The randomisation schedule was known only to the independent university employee, the generating statistician and the unblinded statistician.

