2.3 Sample Size

Total Neuropathy Score was selected to measure the primary endpoint as it met the requirements for neuropathy assessment as articulated in the 2005 Consensus Statement[7]. However, at the time the study was designed, *there were no available results for Total Neuropathy Score assessments in dialysis patients*. Accordingly power calculations were made using information on Neuropathy Symptom Score grades and sural nerve conduction values that were available when the study was designed[3, 8, 9]. Using assumptions based on those studies FINESSE was calculated as having more than 90% power to detect a reduction in moderate to severe neuropathy from 80% in the control arm to 48% prevalence in the treatment arm (absolute difference of 32%) with a sample size of 120 (with $\alpha=0.05$), including an allowance for 20% combined drop-out and loss to follow-up

(n=96 in the final analysis). We also calculated that with 90% power (with $\alpha=0.05$) the study could detect an absolute difference of 2.6mcV in the mean response of sural nerve sensory amplitudes between the treatment groups (assuming a standard deviation of 3.9).

Since developing the original protocol, studies have been conducted that provide data on the Total Neuropathy Score from an external cohort of dialysis patients ([name], personal communication). In 49 dialysis patients, the mean TNS was 9.2 (SD: 7.8) with 42% (20/48) having a TNS score of 17-32 (moderate to severe neuropathy). Using these assumptions, FINESSE has 90% power to detect a mean difference of 5.2 in TNS between treatment arms at the end of the study and 80% power to detect a mean difference of 4.5.

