3.1 Confidence intervals and p values

All tests are two-sided and the nominal level of alpha will be 5%. P-values will not be adjusted for multiplicity.

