 - Timing of dialysis: day/night/combination of both
 - Access: native AVF, synthetic graft, tunnelled catheter, non-tunnelled catheter, other
 - Mode of access: buttonhole cannulation, rope ladder cannulation, Dialysis catheter, other
 - Anticoagulation (heparin, enoxaparin, nil or other and dose)
 - Dialysate composition: Sodium, Potassium, Calcium, Glucose

- Dialysis parameters: blood flow rate, dialysate flow rate, membrane, machine brand and model, dialysate temperature
- Medications
 - Phosphate binders, number and dose

Physical Examination

- Pre-dialysis blood pressure, average of 3 if available
- Height, weight, dialysis ideal body weight, BMI (derived from height and ideal body weight)
- Waist circumference, Hip circumference, Waist:hip circumference (derived from waist and hip circumferences)

Laboratory Measures

- Haematology: Haemoglobin, Total white blood cell count, Platelet count
- Biochemistry: Sodium, Potassium, Chloride, Glucose, Bicarbonate, Creatinine, Calcium (using corrected calcium formula^a), Phosphate (pre-dialysis), Calcium phosphate product (derived from calcium and phosphate), Albumin, C-reactive protein, Parathyroid Hormone
- Pre dialysis and post dialysis Urea, Small molecular clearance reported as either Urea Reduction Ratio or Kt/V
- β_2 -microglobulin levels (pre and post dialysis)
- Total cholesterol, Triglycerides
- Ferritin, Transferrin saturation
- HbA1c (if diabetic)
- Troponin (if available)
- B natriuretic peptide (if available)

^aThe corrected calcium will be calculated according to the following formula:

corrected calcium (in mmol/l) = measured calcium (in mmol/l) + ((40-albumin (g/l))x0.02)

Quality of Life Scores

- EQ-5D
- KDQOL SF-1.3
- KDRL

Neuropathy assessment (Appendix 1)

- Modified Total Neuropathy Score and stratification
- Neuropathy symptom score and Neuropathy symptom score stage, derived from neuropathy symptom score

5 Analysis

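### The access-failure models leave out baseline access type, which the endpoint definition depends on and randomisation does not balance: a cheap improvement of low severity

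*SAP*

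**What the plan says.** SAP 5.2 (Secondary/SAEs outcomes) assigns the models. For counts, including episodes of access failure (2b) and septicaemia (2c): "Count secondary endpoints, such as number of reported access-related AEs, will be modelled using a Poisson regression model", with a switch to negative binomial if dispersion exceeds 1.3. For time to access failure (2a): Kaplan-Meier curves, a log-rank test, and a Cox model if hazards are proportional. No covariate is named for any of these. Section 5.1 says that secondary outcomes follow the approach of the primary model. Even read generously, that would carry over baseline-score terms, not access type.

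Section 5.1 defines access failure as a thrombosis or a fistula that has to be revised. It defines septicaemia as culture-positive septic episodes for which no source was defined.

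Access type is among the baseline variables (section 4.4): "Access: native AVF, synthetic graft, tunnelled catheter, non-tunnelled catheter, other". The subgroup list in section 5.2 (Analysis methods) already reduces it to AVF versus other, because "the clear majority of participants (78%) were using an AVF at baseline". Section 2.2 gives the only stratification factor: "Participants were randomised in a 1:1 fashion with stratification by baseline neuropathy score".

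**The concern.** One of the two events that make up access failure can happen only to a fistula. A participant dialysing through a catheter has no fistula in use to be revised, so access type bears on which events a participant can have. Nothing in the design balances it between arms. Elsewhere the SAP does adjust: the primary model carries baseline score, and non-repeated continuous outcomes are adjusted for their baseline value. An event outcome has no baseline value of its own, and for access failure the baseline access type is the natural substitute.

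At stake is the access-safety comparison of haemodiafiltration with standard dialysis. If the baseline table shows different access mixes in the two arms, the SAP offers no planned adjusted estimate. Any adjustment would then be chosen after the fact, in an open-label trial (section 2.1). The access subgroup analysis does not fill the gap: the SAP does not say that it covers safety outcomes, and an interaction test is not an adjusted overall estimate.

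**Working it through.** **The plan's own figure.** The SAP claims no power for access failure; its power statements concern neuropathy. The main one, to "detect a reduction in moderate to severe neuropathy from 80% in the control arm to 48% prevalence in the treatment arm", "including an allowance for 20% combined drop-out and loss to follow-up", uses 120 × 0.8 = 96 ("n=96 in the final analysis"), or 48 per arm. With mean proportion 0.64:

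z = (0.32 × √48 − 1.96 × √(2 × 0.64 × 0.36)) / √(0.80 × 0.20 + 0.48 × 0.52) = (2.217 − 1.330) / 0.640 = 1.385, power 0.917.

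This agrees with the stated figure of more than 90%, and nothing below changes it.

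**Inputs for this point.** From the SAP: 120 planned, 1:1, 78% on an AVF. Hence 0.22 × 120 = 26.4, taken as 26 not on an AVF, with 60 per arm. The SAP gives no event rate and no ratio of event rates by access type. Those used below are assumptions.

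**Chance imbalance.** If k of the 26 fall in one arm, the difference in non-AVF share is (2k − 26)/60.
- Var(k) = 60 × (26/120) × (94/120) × (60/119) = 5.13, so SD(k) = 2.27 and the SD of the difference is 2 × 2.27/60 = 7.6 points.
- A difference of 10 points or more means k ≤ 10 or k ≥ 16; the hypergeometric probability is 0.27.
- For 15 points or more it is 0.045.

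**Shift from a 10-point imbalance (27% v 17%) with no treatment effect.** If non-AVF access has r times the AVF event rate, the crude ratio is (1 + 0.27(r − 1)) / (1 + 0.17(r − 1)):
- r = 0.5: 0.865/0.915 = 0.95
- r = 2: 1.27/1.17 = 1.09
- r = 3: 1.54/1.34 = 1.15

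The imbalance can fall either way, so the reciprocals are equally likely.

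**Gain from adjustment, by simulation.** 120 participants, 26 not on an AVF, follow-up 1 to 4 years, AVF event rate 0.1 or 0.3 per year, gamma frailty variance 0 or 1 for counts, true treatment ratio 0.6 for power. All are assumed. Spread is given under no treatment effect.

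Count model, with the SAP's 1.3 switch (1,000 runs per setting):

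| r | Rate | Frailty | SD of log rate ratio, without → with access | Power %, without → with |
|---|---|---|---|---|
| 2 | 0.1 | 0 | 0.370 → 0.362 | 26.9 → 26.7 |
| 2 | 0.1 | 1 | 0.400 → 0.399 | 25.0 → 25.1 |
| 2 | 0.3 | 0 | 0.206 → 0.198 | 61.7 → 62.9 |
| 2 | 0.3 | 1 | 0.298 → 0.287 | 41.6 → 45.2 |
| 4 | 0.1 | 0 | 0.334 → 0.306 | 35.5 → 34.7 |
| 4 | 0.1 | 1 | 0.406 → 0.372 | 24.7 → 30.0 |
| 4 | 0.3 | 0 | 0.218 → 0.164 | 60.6 → 76.0 |
| 4 | 0.3 | 1 | 0.306 → 0.266 | 36.6 → 46.7 |

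The SD falls 0-4% at r = 2 and 8-25% at r = 4. Power changes by 0 to +4 and by −1 to +15 points.

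Cox model (600 runs per setting):

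| r | Rate | Median SE, without → with access | Power %, without → with |
|---|---|---|---|
| 2 | 0.1 | 0.369 → 0.372 | 23.3 → 22.7 |
| 2 | 0.3 | 0.245 → 0.247 | 44.3 → 47.2 |
| 4 | 0.1 | 0.336 → 0.339 | 27.0 → 29.7 |
| 4 | 0.3 | 0.237 → 0.240 | 40.3 → 50.0 |

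The SE does not fall. The power gain comes from a log hazard ratio further from zero (for example −0.451 → −0.517 at r = 4, rate 0.3). One power figure near 45% has a Monte Carlo SE of about √(0.45 × 0.55/600) = 2 points.

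**Validity without adjustment (r = 2 to 4).** Type I error was 0.053-0.070 in the count model and 0.042-0.053 in Cox. The mean log rate ratio under no effect lay between −0.009 and 0.018.

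**The case against.** An unadjusted comparison of randomised arms is a legitimate analysis of secondary safety outcomes, and the SAP promises no power for them. A reader might infer that a chance imbalance would pass for a treatment effect, that is, that the analysis is biased. The documents do not support this. The shifts above arise only after conditioning on an imbalance in one direction. Over repeated randomisation the estimate centres on no effect, and the interval largely allows for such shifts: log 1.15 = 0.14 is smaller than every unadjusted SD in the table (0.206 to 0.406). Adjusted count models did not control type I error better (0.044-0.082), although the upper end may reflect the moment estimate of dispersion used. All of this stands.

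It is also fair that the SAP never calls access type a strong predictor. Its definition of access failure could even put the higher rate on the AVF side, since fistula revision needs a fistula. For septicaemia the restriction to episodes without a defined source would remove those traced to the access, which weakens any link. This stands too, and it limits the claim to 2a and 2b.

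Finally, access is tabulated by arm at baseline and at years 1 to 4, so an imbalance would be visible. But seeing an imbalance does not supply a pre-specified adjusted estimate.

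**Conclusion.** The point holds as a modest improvement to the plan, of low severity. It is neither an error nor a contradiction. The models for 2a and 2b omit a baseline variable that bears on the endpoint by definition, is already collected and dichotomised, and is left to chance by the randomisation.

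The size depends on how event rates differ by access type, which the SAP does not give. In the count model the gain is near nil at an assumed ratio of 2 and material only towards 4. A reader might infer that precision is lost in every model; in the Cox analysis of 2a it is not, and the only gain there is in power: −1 to +3 points at a ratio of 2, and +3 to +10 at 4. A ratio below 1 was taken through the shift formula but not simulated. The imbalance probability assumes that the planned 120 were randomised, 60 per arm.

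**What to change.** In SAP 5.2 (Secondary/SAEs outcomes):
- Add baseline access, AVF versus other as in the subgroup list, as a fixed covariate in the count model for 2b and in the Cox model for 2a.
- Stratify the 2a log-rank test by the same variable.
- Report the unadjusted results alongside.
- For 2c, describe an access-adjusted model as supportive, to be fitted only if there are enough events.

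Use access at baseline only; access during follow-up is measured after randomisation.

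The cost is a few lines of SAP text, no new data and one degree of freedom per model. If access type proves unrelated to the outcome, little is lost in the count model: in the simulated settings with a ratio of 1, the SD of the log rate ratio rose by about 1% at most (for example 0.441 → 0.446). The adjusted hazard ratio for 2a is conditional on access type, not marginal, and the report should say so.

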4.3 Participant Follow-up and Withdrawal

All participants were asked to participate in an intervention phase that lasted from randomisation until the earliest of:

- Completion of 48 months in the trial from randomisation, or
- In-centre/ satellite haemodialysis therapy was no longer required (eg patient receives a kidney transplant, transfers to peritoneal dialysis, transfers to home haemodialysis), or
- Transfer to a dialysis unit not able to offer both study interventions, or
- Withdrawal of consent by the participant, or
- Participant death.

Participants withdrawn from the randomised treatment for any reason (either by choice or on advice from their physician) will be followed-up according to the study follow-up schedule and analysed according to the intention-to-treat principle, providing they consent to such follow-up.

The level of withdrawal (to intervention and/or follow-up), timing and reasons for withdrawal will be recorded and presented by treatment group.

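### The count models for safety events name no follow-up-time offset, and Kaplan-Meier for access failure names no handling of death, although time under observation varies

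*SAP*

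**What the plan says.** SAP Section 5.2 (Secondary/SAEs outcomes) states that count endpoints "will be modelled using a Poisson regression model, and a negative binomial model if there is overdispersion (>1.3"). It applies this to 2b (access failure episodes), 2c (septicaemia), 2e (cardiovascular events), 2f (carpal tunnel surgery), 2g (parathyroidectomy) and 2h (fractures). Neither there nor elsewhere does the SAP mention an offset, exposure time, person-years or rates.

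For 2a (time to access failure) and 2d (mortality), "Survival curves and estimated median survival time will be generated according to the Kaplan-Meier method", with a log-rank test and, if hazards are proportional, a Cox model. Section 5.1 defines access failure as thrombosis or a fistula needing revision, so death is not a component. The SAP does not say how death or transplant is treated for 2a.

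Section 4.3 describes an "intervention phase that lasted from randomisation until the earliest of" 48 months, the end of in-centre or satellite haemodialysis (for example through transplant), transfer to a unit that cannot offer both treatments, withdrawal of consent, or death. It adds that participants withdrawn from randomised treatment stay on the follow-up schedule if they consent. Section 2.3 sizes the trial "including an allowance for 20% combined drop-out and loss to follow-up" ("n=96 in the final analysis"). Section 2.2 states: "Participants were randomised in a 1:1 fashion with stratification by baseline neuropathy score".

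**The concern.** A Poisson model without an offset compares events per participant, not events per year observed. A participant who dies event-free at month 3 then counts the same as one who is event-free for 48 months. Mortality is itself an outcome (2d), so mean follow-up could differ by arm. The arm whose participants live longer, or stay longer, would collect more access failures and infections at the same underlying rate, and a survival benefit could look like harm.

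The models also assume Poisson variation around a common mean. Unequal follow-up adds variation of its own, which enters both the standard errors and the 1.3 dispersion threshold that decides which model is fitted.

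For 2a, a participant who has died can no longer have an access failure. One minus Kaplan-Meier with deaths censored estimates the risk in a setting where nobody dies first, and that is higher than the proportion who actually have an access failure.

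**Working it through.** **The plan's own figure.** The SAP gives no figure for the safety analyses. Its only relevant planning figure is the 20% loss: 120 × 0.80 = 96, or 48 per arm. The power stated with it reproduces for 80% v 48%. The pooled SE is √(2 × 0.64 × 0.36/48) = 0.0980 and the unpooled SE is √((0.16 + 0.2496)/48) = 0.0924, so power is Φ((0.32 − 1.96 × 0.0980)/0.0924) = 91.7%, in line with more than 90%. Nothing below rests on this power figure. The 20% is used only as a benchmark for exit, and the SAP does not say whether deaths and transplants are within it.

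**Assumptions.** The SAP gives no event rates or exit hazards. All rates below are assumed, constant over time, with at most 4 years of follow-up.

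**1. Count ratio without an offset.** If the true rate ratio is 1, the fitted ratio tends to the ratio of mean follow-up. With exit hazard h, mean follow-up is (1 − e^(−4h))/h.

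| Assumed exit | Mean follow-up (years) | Fitted ratio |
|---|---|---|
| Equal in both arms | equal | 1.00 |
| 25% v 15% by year 4 | 3.48 v 3.69 | 1.06 |
| 30% v 10% by year 4 | 3.36 v 3.80 | 1.13 |
| Mean follow-up set directly | 2.8 v 3.2 | 1.14 |
| Hazard 0.2 v 0.1 per year | 2.75 v 3.30 | 1.20 |

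**2. Equal exit: standard errors and dispersion.** With event rate r and follow-up time T, the variance-to-mean ratio of the counts is 1 + r × Var(T)/E(T), and the plain Poisson type I error is about 2 × (1 − Φ(1.96/√dispersion)).

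- *20% exit by year 4.* h = −ln(0.80)/4 = 0.0558, E(T) = 3.585, Var(T) = 0.954, ratio 0.266. At 0.2, 0.5 and 1.0 events per year the dispersion is 1.05, 1.13 and 1.27, and the type I error about 5.6%, 6.6% and 8.2%.
- *Exit hazard 0.2 per year (55% by year 4).* E(T) = 2.753, Var(T) = 1.979, ratio 0.719. The dispersion is 1.14, 1.36 and 1.72. A simulation (60 per arm, 4,000 runs, true ratio 1) gave mean dispersion 1.14, 1.36 and 1.73 and type I error 5.6%, 9.0% and 14.1%. Varying follow-up alone exceeded the 1.3 threshold in 14%, 62% and 99% of runs.

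With the offset, the same simulation, including scenarios with unequal exit, gave ratios of 1.00 to 1.01 and type I error of 4.4% to 5.1%. Without it, at hazards of 0.2 v 0.1 per year, plain Poisson type I error was 12% to 45%.

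**3. Access failure at 4 years.** Assumed access-failure hazard λ = 0.15 per year, competing hazard c. Kaplan-Meier with competing events censored gives 1 − e^(−4 × 0.15) = 45.1%. The cumulative incidence is λ/(λ + c) × (1 − e^(−4(λ + c))):

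- c = 0.0558 (20% competing exit by year 4): 0.729 × (1 − e^(−0.823)) = 40.9%
- c = 0.1: 0.600 × (1 − e^(−1.0)) = 37.9%
- c = 0.2: 0.429 × (1 − e^(−1.4)) = 32.3%

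**4. Median time to access failure.** The Kaplan-Meier median is ln 2/0.15 = 4.6 years. At c = 0.1 the cumulative incidence reaches 50% only at ln 6/0.25 = 7.2 years. At c = 0.2 it never does, because its ceiling is 0.15/0.35 = 43%. The Kaplan-Meier median is therefore too short. At this rate it also lies beyond the 4-year window.

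**The case against.** The strongest reply is that the SAP is silent rather than wrong. A reader might infer that it prescribes raw counts and the censoring of deaths. It says neither; both are what the named methods do by default when nothing is added. That reply stands as to wording, but model specification is the SAP's job, and an analyst following this text would fit those defaults.

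A reader might also infer from Section 4.3 that follow-up stops at transplant or transfer. The list there ends the intervention phase, and the next sentences provide for continued follow-up after withdrawal from treatment. Whether that covers transplanted or transferred participants is unclear. Only death and withdrawal of consent to follow-up clearly end observation.

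It is also fair that the larger sizes need heavy loss. Mean follow-up of 3.2 v 2.8 years implies about 37% v 53% exit by year 4, and competing hazards of 0.1 to 0.2 per year remove 33% to 55% of participants. Both are well above the 20% allowance.

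Three further points stand in part. The negative binomial fallback absorbs extra variance when it is triggered, but it does not remove bias from unequal follow-up. Outcome 2e counts cardiovascular deaths as events, so for that outcome a survival benefit would partly offset longer exposure. And these are secondary safety outcomes; the primary analysis is untouched.

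**Conclusion.** The point holds as a gap in the specification that would distort some results if the text were followed literally. The count ratio carries the ratio of mean follow-up: nothing at equal exit, 1.06 at an assumed 25% v 15% exit, 1.14 at an assumed 3.2 v 2.8 years. At equal exit the remaining harm is to plain Poisson standard errors and the dispersion check. That harm is small at 20% exit with rare events and grows with event rate and exit. For 2a, the Kaplan-Meier risk is too high by about 4 percentage points at 20% competing exit and by 7 to 13 points at competing hazards of 0.1 to 0.2 per year, and the median time is too short.

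The documents do not support saying that the safety comparisons will be biased. The count ratio is biased only if mean follow-up differs by arm, and for 2a the log-rank test and Cox hazard ratio still validly compare cause-specific hazards. Mortality (2d) has no competing-death problem. Nor are the unstratified tests invalid because randomisation was stratified by neuropathy score: nothing in the SAP shows that this stratum predicts these events. All sizes rest on assumed rates.

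**What to change.** 1. In Section 5.2, add log(time at risk) as an offset to every Poisson and negative binomial model (2b, 2c, 2e to 2h), assess dispersion with the offset in place, and report rate ratios. Define the window: when time at risk starts and ends, and whether events after transplant, change of modality or transfer count. Reconcile this with Section 4.3.
2. For 2a, report cumulative incidence by arm with death as a competing event (and transplant, if it ends observation). Keep the log-rank test and Cox model, labelled as cause-specific.
3. Optionally, stratify the log-rank and Cox analyses by the randomisation stratum (TNS 0-8 v 9-28), and include it in the count models where event numbers allow.

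The cost is a few sentences in the SAP and slightly more analysis work, with no change to sample size. It needs each participant's start and end of observation. The stratum may have to be dropped for rare events such as 2f and 2g.

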1. The intent of secondary outcome 1b is to evaluate the proportion of people with asymptomatic disease in each group. To allow each assessment to be categorised as either asymptomatic or symptomatic, we have specified a definitive mathematical range for each category, 0-8 and 9-28 respectively. The 0-8 range represents the 'asymptomatic' range which we are more accurately describing here as 'no or minor neuropathy'.

To limit the number of comparisons and risk of Type I error we will only test for differences in binary outcomes where there has been a difference detected ($p < 0.05$) in the analysis of the continuous variable, i.e. analysis of 1b will only proceed if there is a difference in a time point in 1a, and 1d proceeds if we find a difference in 1c.

2) Safety outcomes. Analyses will include:

- a) Time to access failure, defined as thrombosis or fistula requiring revision
- b) Number of discrete episodes of access failure, defined as above.
- c) Episodes of septicaemia defined as blood culture positive septic episode without defined source.

d) Mortality

e) Cardiovascular events (composite of: cardiovascular death or any of the following requiring or occurring during a hospital admission: acute myocardial infarction, cerebrovascular event, percutaneous coronary or cerebrovascular revascularisation, or surgical coronary or cerebral revascularisation)

f) Surgery for carpal tunnel syndrome

g) Parathyroidectomy surgery

h) Fractures requiring or occurring during a hospital admission

3) Durability:

Durability is defined as adherence to the intervention at each time point

4) Ranked composite endpoint combining mortality and TNS

5) Follow-up of long term events.

a) Long-term survival at 24, 36 and 48 months following the conclusion of individual's intervention period

b) Durability of the intervention at 12, 24, 36 and 48 months following the conclusion of individual's intervention period

These events will be analysed during the post-intervention cohort observation period and will be subject to a later Statistical Analysis Plan.

Exploratory analyses:

1) By components of modified TNS: Mean change in score from baseline to end of study for:

a. Clinical symptoms (sensory and motor symptoms)

b. Physical examination (pin sensitivity, strength, tendon reflexes)

c. Nerve conduction study (sural and tibial amplitudes)

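### The bracketed rank order for the death-and-TNS composite (secondary outcome 4) contradicts the prose around it; if it is the order programmed, the treatment effect among survivors changes sign.

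*SAP*

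**What the plan says.** SAP section 5.1 lists secondary outcome 4 as "Ranked composite endpoint combining mortality and TNS". The Composite Rank Score paragraph of section 5.2 (Secondary/SAEs outcomes) defines it:

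- Patients who die before 48 months are "ranked from lowest (poorest outcome) to highest on their survival time (less survival time=lower rank"), so a low rank is a bad outcome.
- Survivors with a TNS then "will be ranked from least to most favourable change in TNS from baseline". The same sentence defines change as the follow-up score minus the baseline score.
- Survivors without a valid TNS are censored. Attached to that sentence is a bracket that writes the whole order as one inequality: "Shortest Survival < Longest Survival < Lowest TNS change < Highest TNS change".
- For the analysis, "Ranks between treatment groups will be compared with a log-rank test", and a Cox model gives the hazard ratio.
- The paragraph closes with its main assumption, that "death at any time is worse than the greatest increase in TNS".

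The direction of the scale is not in doubt. Section 2.2 labels scores of 0 to 8 as no to minor neuropathy and 9 to 28 as moderate to severe, and Appendix 1 labels 25 to 28 as severe.

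**The concern.** The paragraph gives two opposite orders for survivors. Read literally, the lowest change is the most negative one, which is the greatest improvement. The bracket places that patient just above the last death and gives the top rank to the patient with the greatest deterioration. Deaths would run from worst to best and survivors from best to worst on one scale.

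The log-rank test and the hazard ratio use nothing but the order, so the direction decides which arm appears better. Secondary outcome 4 is the only analysis in this SAP that combines death with neuropathy. If the conflict is noticed only after unblinding, someone must choose between two pre-specified directions with the results in view.

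**Working it through.** **1. The statements side by side**

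| Statement in the paragraph | Survivor placed next to death | Survivor given the best rank |
|---|---|---|
| Prose: least to most favourable change | Largest increase in TNS | Largest decrease in TNS |
| Closing assumption: death compared with the greatest increase | Largest increase in TNS | (not stated) |
| Bracketed inequality | Largest decrease in TNS | Largest increase in TNS |

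Two of the three agree with each other and with the scale. The bracket is the exception.

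**2. Small example.** Take five survivors with changes −6, −2, 0, +3 and +8, listed from worst rank to best.

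- Prose: +8, +3, 0, −2, −6.
- Bracket: −6, −2, 0, +3, +8.

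The second list is the first exactly reversed. Deaths are ordered identically in both.

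**3. The plan's own figures.** The SAP gives no power for the composite. Its TNS figures (section 2.3) serve as inputs, and they reproduce.

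- Analysed patients: 120 × (1 − 0.20) = 96, or 48 per arm.
- Power ≈ Φ(δ·√(n/2)/SD − 1.96), with n = 48 per arm and SD = 7.8.
- δ = 5.2: 5.2 × 4.899 / 7.8 = 3.27, and Φ(1.31) = 90.4% (stated: 90%).
- δ = 4.5: 4.5 × 4.899 / 7.8 = 2.83, and Φ(0.87) = 80.7% (stated: 80%).

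**4. Size of the reversal, by simulation.** The same simulated patients were ranked in both orders, and log-rank and Cox were applied to the ranks. Haemodialysis is the reference, so a hazard ratio below 1 means that haemodiafiltration patients reach higher, better ranks.

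Inputs from the SAP: difference 4.5, SD 7.8, two-sided 5% level, and 48 per arm analysed or 60 per arm randomised. Assumptions: 7.8 applies to change; deaths are 20% or 40% and unrelated to arm; in the 60-per-arm runs, 20% of survivors lack a TNS and are censored after the last death. There were 1,000 trials per scenario at 48 per arm and 500 at 60 per arm.

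| Scenario | HR, prose order | HR, bracketed order | Significant for haemodiafiltration, prose order | Significant for haemodialysis, bracketed order |
|---|---|---|---|---|
| 48 per arm, no deaths | 0.58 | 1.70 | 76% | 73% |
| 48 per arm, 20% deaths | 0.65 | 1.54 | 53% | 53% |
| 60 per arm, 20% deaths, censoring | 0.65 | 1.49 | 50% | 44% |
| 48 per arm, 40% deaths | 0.73 | 1.37 | 30% | 32% |
| 60 per arm, 40% deaths, censoring | 0.74 | 1.35 | 29% | 27% |

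Among survivors alone (4.5-point benefit, no effect on death), the hazard ratio is 0.58 to 0.59 in the prose order and 1.70 to 1.76 in the bracketed order. With 40% control deaths and an assumed mortality hazard ratio of 0.7 (48 per arm), the composite moves from 0.63 to 1.24. The share of deaths, and any effect on death, therefore govern how far the whole composite shifts.

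**5. The SD of change.** The 7.8 is a cross-sectional SD from 49 external dialysis patients, whose scores are described on the range up to 32. If the variance is equal at both times and the correlation is ρ, the SD of change is 7.8 × √(2(1 − ρ)). This equals 7.8 at ρ = 0.5. An SD of 5 would need ρ = 1 − (5/7.8)²/2 = 1 − 0.411/2 = 0.79. The SAP gives no correlation.

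**The case against.** The strongest reply is that the intended order can be recovered from the paragraph itself. The sentence that states the ranking rule is right, the closing assumption agrees with it, and only a gloss attached to the censoring sentence is wrong. That stands, and it limits the point to a contradiction. A reader might infer that the plan's ranking simply is reversed, or that whoever programs it will probably follow the inequality. The SAP supports neither: it states the right order too, and nothing in it shows which line will be coded.

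A softer reply is that lowest change was meant as least favourable change. That would remove the conflict, but the paragraph defines change as a signed difference, so the literal reading is the natural one. The text would need correcting even if the benign meaning was intended.

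A third reply is that the consequence is contained. Change in TNS at year 4 (outcome 1a) and mortality (outcome 2d) are reported separately, so a composite that pointed against both would be conspicuous, and no other test depends on outcome 4. This also stands and lowers the severity. It does not remove the need to settle the direction before the results are seen.

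A reader could also find a more dramatic size. With an SD of change of 5, the bracketed order gives a hazard ratio of about 1.9 and significant apparent harm in more than 80% of trials. That SD appears nowhere in the SAP, so those figures are the upper end of a range and not typical values.

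**Conclusion.** The point holds as an internal contradiction in the definition of secondary outcome 4. The bracketed inequality conflicts with the prose, with the definition of change, with the direction of the scale and with the closing assumption, and the SAP does not say which governs. The change of sign among survivors is conditional on the bracket being the order programmed.

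Under the stated assumptions, the wrong order would turn a composite hazard ratio of about 0.65 into about 1.5 with 20% deaths, and about 0.73 into about 1.36 with 40% deaths. In the bracketed order, 44% to 53% and 27% to 32% of trials respectively would be significant in the wrong direction. The 4.5 points is a detectable difference at 80% power and not an expected effect; the death rates, the missing TNS and the use of 7.8 for change are assumptions.

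The primary analysis, the sample size, the yearly TNS analyses, the mortality analysis and the ranking of deaths within the composite are all unaffected. This is a should-fix correction to one secondary endpoint.

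**What to change.** In section 5.2, replace the bracketed inequality with: *Shortest survival < Longest survival < Largest increase in TNS (greatest worsening) < Largest decrease in TNS (greatest improvement); higher rank = better.* Add that haemodialysis is the reference group and that a hazard ratio below 1 favours haemodiafiltration.

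The cost is one or two lines of text, with no new data and no change of method. It should be done before the unblinded analysis. If the composite has already been analysed, check which direction was coded and record the result of that check.
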